**Table 23. Time to tumour progression**

	N	Mean (SD)	Median (Min-Max)
Time to tumour progression (weeks)			

**2.7.2.3 Response duration**

The response duration (RD) will be calculated in those patients with objective response (CR + PR). This is defined as the time between the first recorded objective response (CR or PR), which is subsequently confirmed, to the first objective evidence of radiological progression or death from any cause.

The median of the RD was XXX weeks:

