9. STATISTICAL ANALYSIS

9.1. *Descriptive Analysis*

The descriptive analysis of patient characteristics will include demographic data, disease-specific data and prior treatments. Qualitative data will be described with absolute frequencies and corresponding percentages. Quantitative data will be studied using the mean \pm standard deviation, median, minimum and maximum values. The response percentages will be estimated using confidence intervals of 95%. In the safety analysis, adverse events will be specified according to the maximum grade described at the discretion of the investigator and defined by NCI-CTCAE, version 4.0 (see section 10.2.3.), including adverse events described from treatment initiation until 28 days following its completion.

The following safety analysis data will be presented:

- Temporary and permanent treatment discontinuations due to an adverse event.
- Deaths.
- Adverse Events (AEs) and Serious Adverse Events (SAEs).
- Hospitalisations.
- Use of concomitant medication and growth factors.

9.2. *Inferential Analysis*

The objective response rate corresponding to the percentage of patients in which there is confirmation of a complete response (CR) or a partial response (PR) according to RECIST criteria, in relation to the total analysis population, will include a confidence interval of 95%. The association between the marker expression profiles analysed in plasma and in tumour tissue for treatment response (yes/no) will be assessed using logistic regression models and univariate and multivariate Cox regression, establishing the corresponding *hazard ratio* and confidence interval at 95%. The predictive value (of genetic biomarkers, in plasma and tumour tissue) of each model will be estimated using an area under the ROC curve.

The survival analyses will be performed using the Kaplan-Meier method presented with the corresponding graph, as well as by Cox regression analysis to obtain the *hazard ratios* and confidence intervals for the associations. For patients without documented progression or death at the time of analysis, the PFS will be censored at the last date of tumour assessment. For patients who have not died at the time of analysis, the OS will be censored.

All statistical tests are bilateral, two-tailed tests, and all values with $p < 0.05$ will be considered significant.

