10. ASSESSMENT CRITERIA

10.1. Efficacy Assessment

Objective response rate (ORR)

This will be assessed according to RECIST version 1.1 criteria, to be performed every 8 weeks, regardless of treatment delays caused by treatment toxicity.

The ORR is defined as the percentage of patients in which there is confirmation of a complete response (CR) or a partial response (PR) according to RECIST criteria, in relation to the total analysis population.

A response is confirmed for patients in whom the response persists in an imaging test repeated ≥ 4 weeks after initial documentation of response.

Progression-free survival (PFS)

This is defined as the time between the start of study treatment to the date of first objective evidence of radiological progression or patient death from any cause; whichever comes first.

Time to progression (TTP)

This is defined as the time between the start of study treatment to the date of first objective evidence of radiological progression.

Response duration (RD)

This is defined as the time between the first recorded objective response (CR or PR), which is subsequently confirmed, to the first objective evidence of radiological progression or death from any cause.

RD will only be calculated in the subgroup of patients with objective response (CR + PR).

Overall survival (OS)

This is defined as the time between the start of study treatment to the date of death from any cause. If confirmation of death could not be obtained, survival will be censored with the date of the last visit at which time the patient was known to be alive.

Safety

See Safety Assessment section below.

Biomarkers:

They assess the correlation between radiological response and the patient's clinical course and the following expression levels:

A phase II trial to assess the activity and safety of TH-302 in combination with sunitinib in patients

- ENO1 (enolase 1) in plasma (it will be performed locally at the same time as chromogranin at each participating site)

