#### Response duration (RD)

This is defined as the time between the first recorded objective response (CR or PR), which is subsequently confirmed, to the first objective evidence of radiological progression or death from any cause.

RD will only be calculated in the subgroup of patients with objective response (CR + PR).

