### 2.7.2. Secondary efficacy analysis

The progression free survival will be estimated and plotted using the Kaplan-Meier product-limit method, along with their corresponding log-log transformed 95% confidence intervals

Time to tumour progression, duration of response and overall survival will also be described using these same Kaplan-Meier methods.

Cox regression analysis will be used to obtain hazard ratios and their confidence intervals for the associations. For patients without documented progression or death at the time of analysis, the PFS will be censored at the last date of tumour assessment. For patients who have not died at the time of analysis, the OS will be censored.

The association between the marker expression profiles analysed in plasma and treatment response (yes/no) will be assessed using logistic regression models and univariate and multivariate Cox regression, establishing the corresponding hazard ratio and confidence interval at 95%. The predictive value (of genetic biomarkers, in plasma and tumour tissue) of each model will be estimated using an area under the ROC curve.

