**Table 24. Response duration time**

	N	Mean (SD)	Median (Min-Max)
Response duration time (weeks)			

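### SAP 2.7.2 assigns Kaplan-Meier to response duration, but 2.7.2.3 and Table 24 specify only a plain mean and median, and no censoring rule is stated

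*SAP*

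**What the plan says.** **Method text.** SAP 2.7.2 sets out Kaplan-Meier estimation with log-log 95% intervals for progression-free survival (PFS), then adds: "Time to tumour progression, duration of response and overall survival will also be described using these same Kaplan-Meier methods". Protocol 9.2 is consistent with this: "The survival analyses will be performed using the Kaplan-Meier method presented with the corresponding graph".

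**Definition.** In both documents, response duration (RD) runs from the first recorded response that is later confirmed "to the first objective evidence of radiological progression or death from any cause". Protocol 10.1 limits it to responders ("RD will only be calculated in the subgroup of patients with objective response (CR + PR"), and SAP 2.7.2.3 does the same: "The response duration (RD) will be calculated in those patients with objective response (CR + PR".

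**Output.** SAP 2.7.2.3 reports one summary sentence, "The median of the RD was XXX weeks", followed by Table 24, whose columns are N, mean (SD) and median (min-max). There is no column for events, censored patients, standard error or confidence interval. The SAP's index of figures lists Kaplan-Meier curves for PFS and overall survival (OS) only.

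**Censoring.** SAP 1.5.5.3 and 2.7.2 state censoring rules for PFS (last tumour assessment) and for OS. Neither states one for RD.

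**The concern.** RD ends at progression or death, so a responder who has had neither by the analysis date has no completed duration. A Kaplan-Meier analysis handles that patient by censoring. A mean with SD and a simple median need one completed value per patient. A programmer working from 2.7.2.3 and Table 24 would have to leave the patient out or enter the time to date as if the response had ended.

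The longest responses are the ones most likely to be ongoing, so the error grows as responses last longer. Protocol 3.6 gives better and more durable responses as an aim of the combination, and RD is the endpoint that describes durability most directly. The number of responders may be small: SAP 1.5.4 treats 8 responses among 43 patients as encouraging. An estimate from so few patients needs an interval, and Table 24 has none.

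**Working it through.** **1. Is this only a terse table shell?** Where the SAP intends Kaplan-Meier output, its shells say so.

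| SAP table | Endpoint | Layout |
|---|---|---|
| 21 | PFS | events, at risk, Kaplan-Meier median, standard error, 95% CI |
| 25 | OS | same as Table 21 |
| 20 | Time to response | N, mean (SD), median (min-max) |
| 24 | RD | N, mean (SD), median (min-max) |

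Table 24 has the layout of Table 20. That layout suits time to response, which is fully observed in every responder. It does not suit RD, which may not be.

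**2. Inputs for the size.** The documents give no expected RD, so there is no figure of the plan's own to reproduce.

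- From Protocol 5.3: 24 months' accrual, then 20 months' follow-up, so analysis at month 44.
- From SAP 2.1.2: the report shell names a 2017 database cut-off for a first preliminary analysis. First enrolment is planned for February 2015, so accrual to plan ends about February 2017. A 2017 cut-off is then about 0 to 10 months after accrual.
- Assumed: uniform entry; first response at 2, 4 or 6 months in 50%, 30% and 20% of responders; exponential RD with true median m of 6 to 24 months.

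**3. Formulas.** Let λ = ln 2 / m, let F be follow-up after accrual, and let C = 24 + F − entry time − time to response be the follow-up available after response.

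- Share ongoing = E[exp(−λC)]
- Mean if ongoing responses are counted as ended = (1 − share ongoing) / λ
- True mean = 1/λ = m / ln 2

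**4. Worked case, m = 12 and F = 20.** For a response at t months, C is uniform from 20 − t to 44 − t, and 24λ = 2 ln 2 = 1.386.

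- t = 2: (0.3536 − 0.0884) / 1.386 = 0.191
- t = 4: (0.3969 − 0.0992) / 1.386 = 0.215
- t = 6: (0.4454 − 0.1114) / 1.386 = 0.241
- Weighted: 0.5 × 0.191 + 0.3 × 0.215 + 0.2 × 0.241 = 0.208, so about 21% are ongoing.
- True mean = 12 / 0.693 = 17.3 months. Counted as ended: 17.3 × (1 − 0.208) = 13.7 months.

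**5. Medians and other cases.** These come from simulating the same model, in months.

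| m | F | Ongoing | Median, dropped | Median, counted as ended | Mean, dropped | Mean, counted as ended | True mean |
|---|---|---|---|---|---|---|---|
| 6 | 20 | 5% | 5.6 | 6.0 | 7.4 | 8.2 | 8.7 |
| 12 | 20 | 21% | 8.7 | 12.0 | 10.5 | 13.7 | 17.3 |
| 18 | 20 | 35% | 10.3 | 17.0 | 11.9 | 17.0 | 26.0 |
| 24 | 20 | 45% | 11.2 | 19.5 | 12.7 | 19.1 | 34.6 |
| 12 | 10 | 37% | 6.6 | 9.6 | 8.0 | 10.9 | 17.3 |
| 12 | 0 | 58% | 4.6 | 6.0 | 5.7 | 7.2 | 17.3 |

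With first response spread evenly over 2 to 6 months instead, the m = 12, F = 20 row becomes 22% ongoing, medians 8.6 and 12.0, and a counted-as-ended mean of 13.6. The counted-as-ended median at F = 0 to 10 becomes 5.9 to 9.4. In that version Kaplan-Meier returns the true median in every case, except that the median is not reached at m = 24, F = 0.

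**6. Why one cell shows no bias.** At F = 20 the shortest follow-up after a response is 20 − 6 = 14 months. No response is cut off before 12 months, so counting ongoing responses as ended leaves a 12-month median untouched. The mean has no such protection.

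**The case against.** The strongest reply is that the right method is already in the SAP. Section 2.7.2 names Kaplan-Meier for duration of response, an unfilled shell does not revoke it, and the reference to the same methods could be read as carrying the PFS censoring rule across. This has force. The plan contains the correct method, and the defect is that its specified output does not deliver it. But carrying the rule across is an inference, and a mean with SD is not Kaplan-Meier output. The two parts cannot both be followed as written.

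A reader might go further in four ways that the documents do not support.

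- **That the SAP instructs ongoing responses to be dropped or counted as ended.** It says neither. Section 2.7.2.3 limits RD to responders, not to responders whose response has ended. The two handlings are what the table layout and the missing rule leave open.
- **That the reported duration must be too short.** There is no error if no response is ongoing. The median is also almost unbiased if ongoing responses are counted as ended, follow-up is full and the true median is no more than about 12 months.
- **That restricting RD to responders is the fault.** The restriction matches Protocol 10.1 and is correct.
- **That RD tests whether the combination lengthens responses.** In a single-arm trial it describes durability and makes no comparison.

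It is also fair to say that Table 23 (time to progression) has a similar conflict with 2.7.2, in a more explicit form, because 2.7.2.2 limits that endpoint to patients who progressed. The two can be corrected together, but changing Table 23 would not change Table 24.

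**Conclusion.** The inconsistency stands on the text alone: SAP 2.7.2 promises Kaplan-Meier for RD, while 2.7.2.3 and Table 24 specify an output that cannot accommodate ongoing responses, with no stated rule for them.

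The effect is conditional on some responses being ongoing. Given that, a plain mean is too low under either handling. A plain median is too low if ongoing responses are dropped: 8.7 against 12 months at full follow-up, a shortfall of (12 − 8.7)/12, or about 27%. If they are counted as ended, the median holds at full follow-up for a true value up to about 12 months. It falls short for long responses (19.5 against 24, about 19%) and at an early cut-off (about 6 to 9.6 against 12, or 50% to 20% short).

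These sizes rest on assumed exponential durations, assumed response timing and accrual to plan. They illustrate direction and scale and do not forecast this trial's result. RD is a secondary endpoint and the response-rate decision does not depend on it, but the shell should be corrected before it is used.

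**What to change.** In SAP 2.7.2.3, state that RD is estimated by Kaplan-Meier, and that responders without progression or death are censored at their last tumour assessment, as for PFS. Rebuild Table 24 to show:

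- number of responders;
- number of events, split into progression and death;
- number censored;
- Kaplan-Meier median with log-log 95% CI, shown as not reached where that applies.

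Delete the mean (SD), and add the curve to the section and to the index of figures. Rates at fixed times such as 6 and 12 months are optional: with about 8 responders the intervals will be wide.

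The cost is a short change of SAP wording, one table shell and one figure. It needs no new data, because progression, death and tumour-assessment dates are already required for PFS. Table 23 can be aligned with 2.7.2 in the same revision.

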**Table 24. Response duration time**

	N	Mean (SD)	Median (Min-Max)
Response duration time (weeks)			

**2.7.2.4 Overall survival**

The overall survival rate will be estimated and plotted using the Kaplan-Meier product-limit method, along with their corresponding log-log transformed 95% confidence intervals.

In the total analysis population (n=XX), at 3 months the proportion of patients that survived was XXXX with a 95% CI XXXX-XXXX. The overall median of OS was XXX months (95% CI XXX-XXX).

**Table 25. Overall survival**

[figure not shown]
OS	N events	Patients at risk	% estimated cumulative survival ratio 	95% CI	% exitus
at 3 months					
at 6 months					
at 12 months					
	N	N (%) events	Median (months)	Standard error	95% CI
Estimated OS 					

1: Estimated using Kaplan-Meier product-limit method

**Table 26. Overall survival events**

OS event	N (%; IC 95%)	
	No exitus at end of follow-up	
	Exitus	Total

**Figure 6 Kaplan Meier curve: OS**

### 2.7.2.5 Biomarkers

In the total analysis population (n=XX), the proportion of patients with the following expression levels:

- ENO1 (enolase 1) in plasma (it will be performed locally at the same time as chromogranin at each participating site)
- SNPs (single nucleotide polymorphisms) related to the activity and metabolism of sunitinib and TH-302 VEGFR2 (rs2305948 and rs1870377), VEGFR3 (rs307826), IL8 (rs1126647), CYP3A4 (rs35599367 and rs67666821), CYP3A5 (rs776746), ABCB1 (rs1045642, rs1128503 and rs2032582), POR (rs1057868 and c.1705\_1706insG). If a polymorphism of particular relevance and related to the effectiveness of sunitinib or TH-302 appears in the literature as the study progresses, its inclusion in the study could be considered.
- Hypoxia markers related to paraffin-embedded tumour tissue (HIF1-  $\alpha$ , CYP2W1 and c-Myc).

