3.5. Biomarkers

To date, no validated predictive marker has been identified in pancreatic neuroendocrine tumours. The importance of this research lies in being able to identify patients optimally to ensure as personalised a global approach as possible.

Although VEGF is considered to be the driving force behind angiogenesis in pNET, many studies have proven the involvement of other molecules such as PDGF, cKIT or mTOR. Initial data from patients with neuroendocrine tumours treated with sunitinib (33), (34) has been obtained by measuring circulating biomarker levels in the plasma, such as VEGF, soluble VEGF receptor-2 (sVEGFR-2), interleukin-8 (IL-8) and sVEGFR-3. In one of the studies, sVEGFR-2 and sVEGFR-3 levels dropped significantly by 30% after the first cycle, in 60% and 70% of patients, respectively. The reduction in sVEGFR-3 levels in the first cycle was greater in the subgroup of patients with partial response (N = 11). Elevated IL-8 levels were also identified in those patients with reduced tumour size.

Recently, a phase II study in pNET patients in first line or after progression and treated with pazopanib at a dose of 800 mg/24h, also included a biomarker expression analysis (35). Patients with some degree of VEGFR-2 expression tended towards longer PFS compared to those who did not express this protein (median 12.18 vs. 11.56 months; HR 0.95).

In 101 patients with a renal cell carcinoma treated with sunitinib, 16 SNPs (single nucleotide polymorphisms) have been evaluated, belonging to 9 genes that affect the pharmacodynamics [VEGFR2 (rs2305948, rs1870377), VEGFR3 (rs307826, rs448012, rs307821), PDGFR- α (rs35597368) and VEGF-A (rs2010963, rs699947, rs1570360) and IL8 (rs1126647), and pharmacokinetics [CYP3A4 (rs2740574), CYP3A5 (rs776746)], transport [ABCB1 (rs1045642, rs1128503, rs2032582) and [ABCG2 (rs2231142)] and metabolism [CYP3A5*1, CYP3A4] of sunitinib. The results defined a possible group of patients with VEGFR3 and CYP3A5*1 polymorphisms who had a lower response and worse tolerance to sunitinib (36).

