The HIF-1 pathway is a crucial angiogenesis regulator involving other molecules such as VEGF, PDGF, angiopoietins (Ang-1 and Ang-2), DLL4 and metalloproteinases (37). Carbonic anhydrase (CAIX) is another factor associated with the activity of HIF-1 α and which regulates tumour pH and cell survival, together with cell adhesion. The expression of these key proteins in tumour hypoxia and their determination in pNET patients where this phenomenon is widely described, may contribute predictive information for incorporation in clinical practice.

Finally, TH-302 has been associated with hypoxia, which is why hypoxia markers (vascular microdensity, carbonic anhydrase IX, etc.) are potential candidates to predict which patients will be more likely to respond and which are not.

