8. METHODOLOGY

8.1. Translational Section. Determination of Biomarkers.

Sample Collection

Tumour block collection

A paraffin-embedded tumour block will be requested and sent to [REDACTED] for the hypoxia marker expression study.

Collection of peripheral blood samples

10 ml of peripheral blood will be taken from each patient during the baseline visit and placed in EDTA tubes, to be sent to the Spanish National Cancer Research Centre for polymorphism study.

Handling and storage of samples

Tumour block

The paraffin blocks will be stored at room temperature under routine site conditions after the patient has signed the informed consent form, at which point they will be sent to the reference site.

Peripheral blood samples

The blood samples will be stored at -20 °C from the moment of extraction, and will be sent periodically to the reference site.

Sample shipping

Tumour block

The paraffin blocks will be sent with the periodic deliveries at room temperature (< 25 °C).

Peripheral blood samples

The blood samples will be sent all together and correctly identified in dry ice to the reference site.

Centralised receipt of samples

The paraffin-embedded tumour samples will be received by [REDACTED]

The samples will be received from Monday to Friday, from 08:00 to 15:00.

Peripheral blood samples will be received by [REDACTED] for the attention of:

The samples will be received from Monday to Friday, from 08:00 to 15:00.

Sample processing

Tumour block

The paraffin blocks will be analysed by specialised pathologists as they are received. The expression of hypoxia-related proteins such as CAIX, HIF2A/HIF-1alpha, VEGF, CYP2W1 and c-myc will be assessed centrally and retrospectively in immunohistochemistry.

Peripheral blood:

DNA will be isolated from the peripheral blood, following the instructions of the “FlexiGene DNA kit” (Qiagen), and the concentration of the DNA extracted will be quantitated by the “PicoGreen® dsDNA quantitation reagent” (Invitrogen). The DNA will be stored at -20 °C until genotyping.

Genotyping will be carried out by standard techniques (for example, “TaqMan Probes”, or “KASPar SNP Genotyping System”) using 15 ng of genomic DNA. Fluorescence detection and allele assignment will be performed using the “7900HT Detection System” by Applied Biosystems. The results obtained will be used to create a genetic database, which will collect the genotypes of each patient enrolled in the study.

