- SNPs (single nucleotide polymorphisms) related to the activity and metabolism of sunitinib and TH-302 *VEGFR2* (rs2305948 and rs1870377), *VEGFR3* (rs307826), *IL8* (rs1126647), *CYP3A4* (rs35599367 and [rs67666821](#)), *CYP3A5* (rs776746), *ABCB1* (rs1045642, rs1128503 and rs2032582), *POR* (rs1057868 and c.1705_1706insG). If a polymorphism of particular relevance and related to the effectiveness of sunitinib or TH-302 appears in the literature as the study progresses, its inclusion in the study could be considered.
- Hypoxia markers related to paraffin-embedded tumour tissue (HIF1- α , CYP2W1 and c-Myc).

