5. Clinical chemistry: AST, ALT, GGT, alkaline phosphatase, direct and total bilirubin, urea, calcium, chloride, creatinine, glucose, LDH, phosphorus, magnesium, potassium, sodium, albumin at the baseline visit (≤ 7 days) and at each pre-treatment visit (± 3 days prior to day 8 and ± 1 day prior to day 22 of each cycle). It will also be conducted ± 1 day prior to day 15 to ensure a weekly follow-up of the patients.
6. Enolase 1, chromogranin A (or peptide secreted functionally) tumour markers at baseline visit, every 8 weeks (± 1 week) and at the end-of-study visit.
7. Urine and blood pregnancy test in female patients of childbearing age. This will be conducted within 7 days prior to the day 1 visit and whenever pregnancy is suspected.
8. 12-lead electrocardiogram: before every test, the subject must be at rest for approximately 10 minutes. The subject should be in a semi-lying or supine position; the same position must be adopted for all subsequent ECG tests.
In the first cycle, an ECG will be performed at day 8 and at day 22 immediately after completion of the TH-302 infusion. Thereafter, an ECG will be performed at the discretion of the investigator
9. Baseline and end-of-study visit echocardiogram, and if clinically indicated.
10. Thoracic, abdominal, and pelvic CT scan within 28 days prior to study enrolment and subsequently every 8 ± 1 weeks and at the end-of-study visit. For tumour reassessments, the same exploratory technique used in the baseline examination must be adopted. A baseline bone scan may be performed within 28 days prior to day 1 of the first cycle, if there is a clinical suspicion of bone metastases. In the event of bone metastases, a reassessment bone scan will be performed every 12 weeks until week 24 and thereafter every 24 weeks until the end of treatment. Margin of ± 14 days with reference to the scheduled visit.
An MRI may only be performed in exceptional circumstances and only in cases when a CT scan is not possible.
11. Blood sample for the analysis of genetic markers that will be sent to [REDACTED]. Only the tubes from the baseline visit will be sent.

A phase II trial to assess the activity and safety of TH-302 in combination with sunitinib in patients

12. Paraffin-embedded tumour sample for marker analysis that will be sent to [REDACTED]
[REDACTED]

13. Determination of overall survival of patient (living/death/lost to follow-up). According to the site's usual practices, until the end of the trial.

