**Table 27. Biomarkers**

	N (%; IC 95%)
ENO1	Yes
	No
	Total
VEGFR2	Yes
	No
	Total
VEGFR3	Yes
	No
	Total
IL8	Yes
	No
	Total
CYP3A4	Yes
	No
	Total
ABCB1	Yes
	No
	Total
POR	Yes
	No
	Total
HIF1- $\alpha$	Yes
	No
	Total
CYP2W1	Yes
	No
	Total
c-Myc	Yes
	No
	Total

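### SAP Tables 27-33 have no CYP3A5 row, fold nine variants in four genes into undefined Yes/No rows, and reduce enolase 1 to Yes/No without a cut-off or time point

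*SAP*

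**What the plan says.** **Genotypes.** Protocol 8.1, protocol 10.1 and SAP 1.5.2 and 2.7.2.5 give the same list of variants. It includes "CYP3A4 (rs35599367 and rs67666821), CYP3A5 (rs776746), ABCB1 (rs1045642, rs1128503 and rs2032582"), together with variants in VEGFR2, VEGFR3, IL8 and POR.

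**Tables.** The shell headed "Table 27. Biomarkers" has ten rows, each Yes/No: ENO1, VEGFR2, VEGFR3, IL8, CYP3A4, ABCB1, POR, HIF1-alpha, CYP2W1 and c-Myc. The same ten rows recur in Tables 28-33, which cover the univariate and multivariate models for ORR, PFS and OS.

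**Rationale.** Protocol 3.5 reports, from 101 patients with renal cell carcinoma treated with sunitinib: "The results defined a possible group of patients with VEGFR3 and CYP3A5*1 polymorphisms who had a lower response and worse tolerance to sunitinib".

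**Enolase 1.** SAP Table 6 summarises it with N, mean (SD) and median (range). Protocol Annex 1, note 6, schedules the "tumour markers at baseline visit, every 8 weeks" and again at the end-of-study visit. Protocol 10.1 and SAP 1.5.2 say that each site measures it locally.

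**Tissue.** Protocol 8.1 states: "The expression of hypoxia-related proteins such as CAIX, HIF2A/HIF-1alpha, VEGF, CYP2W1 and c-myc will be assessed centrally". Protocol 10.1, under "Hypoxia markers related to paraffin-embedded tumour tissue", names only HIF1-alpha, CYP2W1 and c-Myc, and the SAP repeats that shorter list.

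**The concern.** The table shells are the only place where the SAP says how each biomarker enters an analysis. Three things follow from them.

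- A gene that the protocol singles out in its rationale has no univariate row. Because SAP 2.7.2.6 to 2.7.2.8 admit markers to the multivariate models on their univariate p-value, it has no route into those models or the ROC curves built on them either.
- A row labelled ABCB1 with the values Yes and No does not say which of three variants, which allele, or how many copies make a patient Yes. The choice would be open after the data are seen, and a single row cannot show which variant carries an effect or whether two variants act in opposite directions.
- Enolase 1 has neither a threshold nor a visit, so its Yes/No value is also open, and dichotomising discards information in a small trial.

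At stake is the interpretability of a listed secondary objective, the prognostic or predictive value of the biomarkers, for which SAP 1.5.5.3 calls any p below 0.05 significant. The primary response-rate analysis does not depend on any of this.

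**Working it through.** The plan states no power or sample size for the biomarkers, so there is no figure to reproduce. The check is a count, an illustration and a cost.

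**1. Variants listed against rows provided** (SAP 2.7.2.5 and Tables 27-33)

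| Gene | Variants listed | Rows in Tables 27-33 |
|---|---|---|
| VEGFR2 | 2 | 1 |
| VEGFR3 | 1 | 1 |
| IL8 | 1 | 1 |
| CYP3A4 | 2 | 1 |
| CYP3A5 | 1 | 0 |
| ABCB1 | 3 | 1 |
| POR | 2 | 1 |
| Total | 12 | 6 |

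- Variants with a row of their own: VEGFR3 1 + IL8 1 = 2.
- Variants sharing a row: 2 + 2 + 3 + 2 = 9, in 4 rows.
- Variants with no row: CYP3A5, 1.
- Check: 2 + 9 + 1 = 12.

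**2. What merging could cost (assumed inputs).** The documents give no carrier frequencies, effect sizes or combining rule. I assume:

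- 43 patients (SAP 1.5.4). This is an upper bound, because protocol 5.1 takes blood only from those consenting to the translational sub-study.
- One active variant, with response 40% in its carriers and 10% in all others.
- k independent variants in the row, each carried by a fraction q.
- Yes means carrying any of them; two-sided 0.05.

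The Yes group is then a fraction a = 1 - (1 - q)^k of patients, with response rate [q × 0.40 + (a - q) × 0.10] / a. For q = 0.30 and k = 2: a = 1 - 0.70² = 0.51, and the rate is (0.30 × 0.40 + 0.21 × 0.10) / 0.51 = 0.276, against 0.10 in the No group. Power is from the normal approximation for two proportions, which is rough at this size.

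| q | Own row (k = 1) | Two merged | Three merged |
|---|---|---|---|
| 0.20 | 0.56 | 0.31 | 0.19 |
| 0.30 | 0.62 | 0.31 | 0.16 |
| 0.50 | 0.63 | 0.21 | 0.07 |

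The direction holds across the range: under this rule, merging dilutes the contrast. The sizes belong to the assumptions, not to the trial.

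**3. Tissue lists side by side.** Protocol 8.1 names CAIX, HIF2A/HIF-1alpha, VEGF, CYP2W1 and c-myc, which is 6 markers if the slash separates two assays and 5 if not. Protocol 10.1 and the SAP name 3. The markers without an analysis are CAIX, VEGF and, if separate, HIF2A: 3 or 2.

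**4. Number of univariate tests over ORR, PFS and OS**

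- Now: 10 rows × 3 = 30.
- One row per variant: (12 variants + enolase 1 + 3 tissue markers) × 3 = 16 × 3 = 48.
- With the extra tissue markers: 18 × 3 = 54 or 19 × 3 = 57.

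Expected false positives at 0.05 if no marker matters: 30 × 0.05 = 1.5; 48 × 0.05 = 2.4; 57 × 0.05 = 2.85. The chance of at least one, if tests were independent, is 1 - 0.95^30 = 0.785, 1 - 0.95^48 = 0.915 and 1 - 0.95^57 = 0.946. The endpoints are correlated, so these probabilities are only a guide.

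**The case against.** The strongest reply is that these are empty shells in a report template. The SAP names CYP3A5 rs776746 in the text directly above Table 27, so the missing row is probably clerical. The rationale for it is also modest: a different tumour, and only a possible group of patients. Both points are fair. The omission nevertheless repeats in every table, and no other text says how CYP3A5 will be analysed, so it needs correcting whatever its cause.

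It can also be said that merging is inferred, since no combining rule is written. That stands in part: the documents do not show that variants will be pooled in any particular way. What they do show is one binary row for two or three variants, which cannot report them separately.

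Three stronger readings are tempting and are not supported:

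- A reader might infer that the plan cannot test the protocol's own biomarker hypotheses. No formal biomarker hypothesis, effect size or power is stated, and VEGFR3, IL8, HIF1-alpha, CYP2W1 and c-Myc each keep a row.
- A reader might infer that the SAP discards assayed tissue markers. Protocol 3.5 does say that "hypoxia markers (vascular microdensity, carbonic anhydrase IX, etc.) are potential candidates to predict which patients will be more likely to respond", and CAIX has no analysis. But the SAP follows protocol 10.1, the section that defines the assessment; the list in 8.1 is worded as examples. The conflict is within the protocol.
- A reader might put the loss for enolase 1 at about a third of the information, since a median split of a normal marker keeps 2/π, or 64%. The documents give neither a cut-off nor a distribution, so no figure can be attached.

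One objection to the remedy also stands. Enolase 1 is assayed locally and ten sites are planned (protocol 1.8), so pooling raw values would assume comparable assays.

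**Conclusion.** The point holds in a limited form. CYP3A5 has no tabulated analysis in any of seven tables. Nine of the 12 variants share four undefined Yes/No rows, so their separate effects cannot be seen. Enolase 1 is binary without a threshold or visit. These are counts from the documents and rest on no assumption.

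The loss of power from merging is an illustration only: in the assumed range, from 0.56-0.63 for a variant in its own row to 0.21-0.31 for two merged and 0.07-0.19 for three. The tissue-marker gap is a separate mismatch between protocol 8.1 and 10.1. Nothing here affects the primary endpoint, and the importance is low.

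**What to change.** 1. In Tables 27-33, add CYP3A5 rs776746 and replace the gene rows with one row per variant. State the genetic model for each beforehand (carrier or allele count, and the reference allele). The documents give no allele frequencies, so also state how a variant with very few carriers will be reported.
2. Analyse baseline enolase 1 as a continuous value scaled to each site's upper limit of normal, for example the log of the ratio. Confirm that the local limits are recorded. If a Yes/No version is kept, state its cut-off and visit.
3. State a positivity rule for the tissue rows that remain.
4. Reconcile protocol 8.1 with protocol 10.1 and the SAP: either add CAIX, VEGF and HIF2A to the analysis or take them out of 8.1.
5. Label the biomarker analyses exploratory, or adjust for multiplicity, and drop the plain 0.05 significance wording for them.

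Items 1 to 3 and 5 are SAP edits on measurements already planned. Item 4 may need a protocol amendment. The price is more tests: 48 instead of 30, or 54-57 with the added tissue markers, which is why item 5 belongs with the others.
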